8.3.4 Adverse event data collection

The following variables will be collected for each AE:

- AE (verbatim)
- The date when the AE started and stopped
- The maximum CTCAE grade reported
- Changes in CTCAE grade (report only the maximum CTCAE grade for a calendar day)

- Whether the AE is serious or not
- Investigator causality rating against the IPs (yes or no)
- Action taken with regard to IPs
- Administration of treatment for the AE
- Outcome

In addition, the following variables will be collected for SAEs:

- Date the AE met criteria for SAE
- Date the Investigator became aware of the SAE
- Seriousness criteria
- Date of hospitalization
- Date of discharge
- Probable cause of death
- Date of death
- Whether an autopsy was performed
- Causality assessment in relation to study procedure(s)
- Causality assessment in relation to other medication, as explained in Section 8.3.5
- Description of the SAE

The grading scales found in the revised NCI CTCAE version 5.0 will be utilized for all events with an assigned CTCAE grading. For those events without assigned CTCAE grades, the recommendation in the CTCAE criteria that converts mild, moderate, and severe events into CTCAE grades should be used. A copy of the CTCAE version 5.0 can be downloaded from the Cancer Therapy Evaluation Program website (<http://ctep.cancer.gov>).

8.3.5 Causality collection

The Investigator will assess causal relationship between Investigational Product and each Adverse Event, and answer yes or no to the question Do you consider that there is a reasonable possibility that the event may have been caused by the investigational product?

For SAEs, causal relationship will also be assessed for other medication and study procedures. Note that for SAEs that could be associated with any study procedure the causal relationship is implied as ‘yes’.

A guide to the interpretation of the causality question is found in Appendix B to the Clinical Study Protocol.

8.3.6 Adverse events based on signs and symptoms

All AEs spontaneously reported by the patient or reported in response to the open question from the study site staff, or revealed by observation will be collected and recorded in the CRF. When collecting AEs, the recording of diagnoses is preferred (when possible) to recording a list of signs and symptoms. However, if a diagnosis is known and there are other signs or symptoms that are not generally part of the diagnosis, the diagnosis and each sign or symptom will be recorded separately.

8.3.7 Adverse events based on examinations and tests

The results from the Clinical Study Protocol mandated laboratory tests and vital signs will be summarized in the CSR. Deterioration as compared to baseline in protocol-mandated laboratory values, vital signs should therefore only be reported as AEs if they fulfil any of the SAE criteria or are the reason for discontinuation of treatment with the investigational product.

If deterioration in a laboratory value/vital sign is associated with clinical signs and symptoms, the sign or symptom will be reported as an AE and the associated laboratory result/vital sign will be considered as additional information. Wherever possible the reporting Investigator uses the clinical, rather than the laboratory term (eg, anemia versus low hemoglobin value). In the absence of clinical signs or symptoms, clinically relevant deteriorations in non-mandated parameters should be reported as AE(s).

Deterioration of a laboratory value, which is unequivocally due to disease progression, should not be reported as an AE/SAE.

Any new or aggravated clinically relevant abnormal medical finding at a physical examination as compared with the baseline assessment will be reported as an AE unless unequivocally related to the disease under study, see sections 8.3.9 and 8.3.10.

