2.3.2.2 Durvalumab + chemotherapy

The safety and tolerability of the combination of durvalumab plus chemotherapy was evaluated in two early studies evaluating different chemotherapy regimens in patients with solid tumors: AZ study D419SC00001 and CCTG study NCT02537418. In general, the combination of durvalumab plus tremelimumab with chemotherapy appeared tolerable and manageable. On all dose levels, dose delays of durvalumab were mostly for administrative reasons/patient request and neutropenia related to chemotherapy.

In the randomized phase III CASPIAN study, durvalumab + EP was well tolerated with a manageable safety profile as first line treatment for ES-SCLC. The safety profile was consistent with the known profile of all the agents and no new safety signals were identified (Paz-Ares 2019). In summary, regardless of causality, rates of AE of any grade (98.1% vs 97.0%), grade 3 or 4 AE (61.5% vs 62.4%), serious AEs (30.9% vs 36.1%), and those leading to discontinuation (9.4% vs 9.4%) were similar between durvalumab + EP vs EP alone. Adverse events of any cause leading to death occurred in 13 (5%) and 15 (6%) patients. The most common adverse events were haematological toxicities. Immune-mediated adverse events, defined as an event that is associated with drug exposure and consistent with an immune-mediated mechanism of action, where there is no clear alternate aetiology and the event required treatment with systemic corticosteroids or other immunosuppressants and/or, for specific endocrine events, endocrine therapy, were reported by 19.6% of patients treated with durvalumab + EP compared to 2.6% of patients treated with EP alone. The majority of immune-mediated AEs were low grade and thyroid related, consistent with the known safety profile of durvalumab.

External clinical data also supports these findings. In the randomized Phase III study IMpower133 demonstrated that the safety profile of atezolizumab combined with etoposide plus carboplatin was consistent with the previously reported safety profile of the individual agents, with no new findings observed (Horn 2018).

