3. OBJECTIVES AND ENDPOINTS

Table 3 Study objectives

Primary Objective:	Endpoint/Variable:
To describe safety profile of durvalumab in combination with platinum–etoposide as first-line treatment for patients with ES-SCLC and also as monotherapy maintenance treatment.	Incidence of grade ≥ 3 AEs Incidence of imAE

Secondary Objective:	Endpoint/Variable:
To describe effectiveness of durvalumab in combination with platinum–etoposide as first-line treatment for patients with ES-SCLC.	Progression Free Survival (PFS). PFS rate at 6 months and at 1 year (PFS6, PFS12). Objective Response Rate (ORR): using site investigator assessments according to RECIST 1.1. Duration of Response (DoR) DoR at 1 year (DoR12). Time to Treatment Discontinuation (TTD). Overall Survival (OS). The OS rate at 6, 12 and 18 months. Time to event endpoints measured as time from first Durvalumab dose.
To describe the impact of durvalumab in combination with platinum–etoposide as first-line treatment for patients with ES-SCLC on patients’ disease-related symptoms and Health Related Quality of Life (HRQoL) and (PROs).	Changes in vital signs, physical findings, and clinical laboratory results during and following study treatment administration Change from baseline in European Organisation for Research and Treatment of Cancer Quality of Life Questionnaire Core 30 items (EORTC QLQ-C30). Change from baseline in European Organisation for Research and Treatment of Cancer Quality of Life Questionnaire-Lung Cancer 13 (EORTC QLQ-LC13).
To describe health care resources use related to management of ES-SCLC patients treated with durvalumab in combination with platinum–etoposide as first-line treatment.	Changes from baseline in PRO-CTCAE. 
- Number and length of hospitalizations- Number of visits to oncology service- Number of emergency visits- Number of outpatient visits- Number of imaging tests- Number of biopsy-related procedures- Treatment dose, duration, number of cycles

Secondary Objective:	Endpoint/Variable:

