^d Creatinine clearance will be calculated by data management using Cockcroft-Gault (using actual body weight).

^e If TSH is measured within 14 days prior to Day 1 (first infusion day), it does not need to be repeated at Day 1.

^f Free T3 or free T4 will only be measured if TSH is abnormal or if there is a clinical suspicion of an AE related to the endocrine system.

ALT Alanine aminotransferase; AST Aspartate aminotransferase, TSH Thyroid-stimulating hormone.

Table 9 Hematology

Absolute neutrophil count ^a	Absolute lymphocyte count ^a
Hemoglobin	Platelet count
Total white cell count	

Note: For coagulation parameters, activated partial thromboplastin time [either as a ratio or as an absolute value, in seconds] and international normalized ratio are to be assessed at baseline on Day 1 (unless all screening laboratory hematology assessments are performed within 3 days prior to Day 1), and as clinically indicated.

^a Can be recorded as absolute counts or as percentages. Absolute counts will be calculated by Data Management if entered as percentage. Total white cell count therefore has to be provided.

Table 10 Urinalysis

Bilirubin	Ketones
Blood	pH
Color and appearance	Protein
Glucose	Specific gravity

Note: Urinalysis should be done at baseline (screening) and then as clinically indicated.

Note: Microscopy is preferred to investigate white blood cells, with use of high power field for red and white blood cells; dipstick can be used as well.

If a patient shows an AST or ALT $\geq 3 \times$ ULN together with total bilirubin $\geq 2 \times$ ULN, refer to 0 for further instructions on cases of increases in liver biochemistry and evaluation of Hy's Law. These cases should be reported as SAEs if, after evaluation, they meet the criteria for a Hy's law case or if any of the individual liver test parameters fulfill any of the SAE criteria.

All patients should have further chemistry profiles performed at 30 days (± 3 days), 2 months (± 1 week), and 3 months (± 1 week) after permanent discontinuation of IP (see the SoAs).

Any clinically significant abnormal laboratory values should be repeated as clinically indicated and recorded on the eCRF. Situations in which laboratory safety results should be reported as AEs are described in Section 8.3.7.

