9.2 Sample size determination

This is a safety study, and given the real-world setting, there is no formal predefined statistical hypothesis and no formal sample size calculation will be done.

A convenience sample size of approximately 85 patients was estimated based on the expected accrual potential during 6 months in 30 sites, although the recruitment duration may be reduced or extended, until P&R approval of durvalumab in Spain for ES-SCLC based on CASPIAN results. Therefore the number of patients recruited could be higher than 85 patients. A maximum of 30% of recruited patients will have ECOG performance status of 2 at baseline.

Assuming a sample size up to 85 and a 70% incidence of AE of CTCAE grade ≥ 3 , the estimated precision will be no wider than 10% based on exact method (Clopper-Pearson). In addition, assuming a 20% incidence of imAE, the estimated precision will be no wider than 9% using the same method. An illustration of the precision around the varying incidences of AE for the patients enrolled is provided in Table 12.

Table 11. Precision around varying incidence of AE

Precision of estimates of G3+ or imAE for varying Sample Sizes using Exact Binomial 95% CI				
Sample size	True rate of Grade 3+ AE or imAE (%) and 95% CI			
	20%	25%	60%	70%
85	$\pm 9.0\%$ 12.1-30.1	$\pm 9.7\%$ 16-35.3	10.9% 48.8-70.5	$\pm 10.0\%$ 59.7-80.0

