9.5.2 Analysis of the secondary variables

9.5.2.1 Safety variables

Adverse events

Total SAEs, AESIs, AEs leading to death, and AEs leading to study drug interruption or discontinuation will be summarized by Medical Dictionary for Regulatory Activities (MedDRA) by system organ class and preferred term, causality, and maximum NCI CTCAE Grade. Deaths from all causes will be also summarized.

Data from all cycles of will be combined in the presentation of safety data. AEs (both in terms of MedDRA preferred term and CTCAE grade) will be listed individually by patient. Any AE occurring before treatment with IP will be included in the data listings but will not be included in the summary tables of AEs. Any AE occurring within 90 days of discontinuation of IP may be included in the AE summaries, but the majority of the AE summaries will omit the AEs observed after a patient has received further therapy for cancer. Further details will be provided in the SAP. Any AE that occurs after a patient has received further therapy for cancer (following discontinuation of IP) will be flagged in the data listings.

For the change from baseline summaries for vital signs, laboratory data, ECGs, and physical examination, the baseline value will be the latest result obtained prior to the first IP dose administration.

The QTcF will be derived during creation of the reporting database using the reported ECG values (RR and QT) using the following formula:

$$QTcF = QT/RR^{(1/3)} \text{ where RR is in seconds}$$

Corrected calcium product will be derived during creation of the reporting database using the following formula:

$$\text{Corrected calcium (mmol/L)} = \text{Total calcium (mmol/L)} + ([40 - \text{Albumin (G/L)}] \times 0.02)$$

The denominator used in laboratory summaries will include only evaluable patients, ie, those who had sufficient data to have the possibility of an abnormality, for example:

- If a CTCAE criterion involves a change from baseline, evaluable patients would have both a predose and at least 1 postdose value recorded.
- If a CTCAE criterion does not consider changes from baseline, to be evaluable, the patient need only have 1 postdose value recorded.

The denominator in vital signs data should include only those patients with recorded data.

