#### Endpoints analyzed:

- Incidence of grade  $\geq 3$  AEs
- Incidence of imAE.

This analysis will be performed for Safety analysis set. For all summaries of AEs, only treatment-emergent AEs will be included. Treatment-emergent AEs are defined as events present at baseline that worsen in intensity after administration of IP or events absent at baseline that emerge after administration of IP, for the period extending to 90 days after the last dose of IP.

The analysis will be performed with the information completed into the adverse event eCRF section.

Total SAEs, AESIs, AEs leading to death, and AEs leading to study drug interruption or discontinuation will be summarized by Medical Dictionary for Regulatory Activities (MedDRA) by System Organ Class (SOC) and Preferred Term (PT), causality, and maximum NCI CTCAE Grade. Deaths from all causes will be also summarized.

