### Endpoints analyzed:

- Incidence of grade  $\geq 3$  AEs
- Incidence of imAE.

Safety data will be summarized descriptively overall, by seriousness, by causality, and by maximum NCI CTCAE Grade. The exact 95% CIs around the incidence of Grade 3 and Grade 4 AEs will be reported. All outputs will be summarized for the Safety analysis set.

A subgroup analysis may be conducted in the following subgroups, assuming sufficient sample size per subgroup: platinum therapy receiving (carboplatin or cisplatin), age, gender, performance status, smoking status and CNS metastasis at baseline (Yes/No).

For this aims, the following summaries of AEs will be provided:

- Number and percentage of patients with AEs in total and by causality and severity
- Number and proportion of patients with Grade 3 and Grade 4 AEs in total and by causality
- Number and proportion of patients with SAEs in total and by causality
- Number and proportion of patients with AEs leading to death
- Number and proportion of patients with AEs leading to treatment interruption and/or discontinuation
- Number and proportion of patients with AESI, by predefined type (or newly defined by this study) in total and by seriousness, severity and causality, including immune relatedness
- Number and proportion of patients who received steroids, immunosuppressants, and/or hormone replacement therapy to manage AESIs
- Time from start of durvalumab to the onset of an AESI predefined type, all interventions of AESIs by type of intervention (including intervention with steroids, immunosuppressants, and/or hormone replacement therapy), and time from onset of an AESI type to resolution.
- Duration of the intervention with steroids, immunosuppressants, and/or hormone replacement therapy until the resolution of AESI.
- Number and proportion of patients with imAEs. The imAEs will be assessed as a subset of AESIs. An imAE is defined as an AESI that is associated with drug exposure and is consistent with an immune-mediated MOA and where there is no clear alternate etiology.
- Listing of SAEs per patient, including the following variables:
  - Patient ID
  - AE number
  - AE description
  - PT Term
  - Grade NCI-CTCAE v5.0 (1-5)
  - Onset date (DD-MMM-YYYY)

- End date (DD-MMM-YYYY)
- Ongoing (Yes; No)
- Outcome
- Seriousness criteria
- AESI (Yes; No)
- Relationship
- Action taken

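### Asymptomatic, non-serious Grade 3-4 laboratory changes are kept off the AE form, and the SAP omits the laboratory summary meant to show them

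*Protocol*

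**What the plan says.** **Reporting rule.** Protocol 8.3.7 first commits to summarising mandated laboratory tests and vital signs in the clinical study report. It then concludes that deteriorations from baseline in these values "should therefore only be reported as AEs if they fulfil any of the SAE criteria or are the reason for discontinuation of treatment"; the treatment meant is the investigational product. If a change is accompanied by signs or symptoms, the sign or symptom is the AE and the laboratory value is supporting information. Haematology is mandated: Table 9 includes "Absolute neutrophil count", haemoglobin and platelets, and Tables 1 and 2 schedule it every cycle and up to 3 months after the last dose.

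**Primary analysis.** SAP 4.2.1 names incidence of Grade ≥3 AEs and of imAEs, and states: "The analysis will be performed with the information completed into the adverse event eCRF section". SAP 5.1 adds: "The exact 95% CIs around the incidence of Grade 3 and Grade 4 AEs will be reported".

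**Laboratory analyses planned in the protocol.**
- Table 3 lists as an endpoint "Changes in vital signs, physical findings, and clinical laboratory results during and following study treatment administration".
- The population table in 9.3 assigns laboratory measurements and vital signs to the safety analysis set.
- Section 9.4, AESI item (e), covers laboratory findings and vital signs associated with AESIs.
- Section 9.5.2.1 describes change-from-baseline summaries and sets CTCAE-based denominators: "The denominator used in laboratory summaries will include only evaluable patients".

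**Laboratory analyses in the SAP.** There are none on treatment. SAP 4.2.2.2 and 5.2.2 cover the questionnaires only. SAP 5.1 carries over AESI items (a) to (d) but not (e). Vital signs appear only at baseline (SAP 4.3.2).

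**The concern.** The reporting rule and the laboratory summary are two halves of one arrangement. The protocol takes uncomplicated laboratory changes off the AE form because it intends to show them elsewhere. The SAP implements the first half and leaves out the second.

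The group affected matters for this regimen. Of the reference phase III trial of the same combination, protocol 2.3.2.2 says: "The most common adverse events were haematological toxicities". Safety is the primary objective here, so a severe cytopenia that is asymptomatic, not serious and handled without stopping treatment is part of what the study sets out to describe. Run as written, the SAP would give no graded incidence for it.

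There is a second source of inconsistency. Appendix B 1 gives an abnormal laboratory finding as an example of an AE. Sites that work from B 1 and sites that work from 8.3.7 could report the same neutrophil count differently, so the recorded incidence would partly reflect which text a site followed.

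**Working it through.** **1. The plan's own figures reproduce.** Section 9.2 starts from "Assuming a sample size up to 85 and a 70% incidence of AE of CTCAE grade" 3 or above. Exact (Clopper-Pearson) 95% intervals at n = 85 are:

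| Count | Recomputed | Stated |
|---|---|---|
| 17/85 (20%) | 12.1-30.1 | 12.1-30.1 |
| 21/85 (25%) | 16.0-35.3 | 16-35.3 |
| 51/85 (60%) | 48.8-70.5 | 48.8-70.5 |
| 60/85 (70%) | 59.7-80.0 | 59.7-80.0 |

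The precision statement is sound. The issue is which events enter the numerator.

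**2. What reaches the AE form under 8.3.7, for a Grade 3-4 change in a mandated laboratory value.**

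| Type of change | On the AE form? | Graded incidence in the SAP? |
|---|---|---|
| Meets an SAE criterion (Appendix B 5 gives transfusion-requiring dyscrasias as an example) | Yes | Yes |
| Causes discontinuation of the investigational product | Yes | Yes |
| Symptomatic | Yes, as the sign or symptom | Yes, possibly under the symptom's term and grade |
| None of these, including changes that lead only to delay or dose reduction | No | No |

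**3. How large the last row could be.** Inputs are the reference-trial rates for durvalumab + EP in protocol 2.3.2.2: Grade 3 or 4 AE 61.5%, serious AE 30.9%, AE leading to discontinuation 9.4%. Even if the last two groups did not overlap and lay wholly within the first,

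P(Grade 3/4 AE, no serious AE, no AE leading to discontinuation) ≥ 61.5 − 30.9 − 9.4 = 21.2%,

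which is 21.2/61.5 = 34% of patients with a Grade 3/4 AE. Let s be the share of that minimum group whose Grade 3/4 events were all asymptomatic laboratory changes. The documents do not give s, so the full range is shown. Recorded rate = 61.5 − s × 21.2:

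| s | Recorded rate | Exact 95% CI at n = 85 (nearest count) |
|---|---|---|
| 0% | 61.5% | 50.0-71.6 (52/85) |
| 50% | 50.9% | 39.5-61.6 (43/85) |
| 100% | 40.3% | 29.5-51.2 (34/85) |

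The 21.2% is a minimum for the group, so 40.3% is not a floor. At s = 0 nothing is lost.

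**4. When the loss would exceed sampling error.** Against the planning rate of 70%, the exact interval excludes 70% once the recorded count is 50/85 or lower (58.8%, CI 47.6-69.4). If the true rate were 70%, that corresponds to 1 − 0.588/0.70 = 16% of Grade ≥3 patients having only unreportable laboratory changes. The 16% is a threshold, not an estimate.

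**The case against.** The strongest reply has four parts.

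*The AE form is the right source for an AE endpoint.* The primary endpoint is incidence of Grade ≥3 AEs, and saying that AE incidence comes from the AE form does not exclude laboratory data from other outputs. This stands. The fault is an incomplete SAP, so the primary endpoint should not be redefined.

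*The protocol still requires the laboratory summaries.* The SAP does not withdraw them, and the study report may contain them. This is true, but protocol 9.4 leaves the specifics of the planned analyses to the SAP, and the SAP lists its outputs without any for laboratory data.

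*Cytopenias that alter dosing would surface.* SAP 4.3.4 tabulates reasons for chemotherapy interruption, delay and reduction, and for durvalumab interruption and, after chemotherapy, delay. This is a partial trace only, with no CTCAE grade and no laboratory denominator.

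*The size is unknown and may be nil.* The documents give neither the laboratory-only share nor the reference trial's reporting rule, and they do not say how the 70% was derived. If both benchmarks already follow the same convention, comparability is not affected. This stands.

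A reader might infer that laboratory changes are barred from AE reporting and that Grade 3-4 haematological toxicity drops out of the primary result. Section 8.3.7 does not say that: serious, treatment-stopping and symptomatic events stay in. Nor are such changes missing from the plan altogether, since the protocol provides for them.

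**Conclusion.** The point holds in a limited form. Asymptomatic, non-serious Grade 3-4 changes in mandated laboratory values that do not cause discontinuation are not reportable as AEs. The separate summary that justifies this rule is in the protocol but not in the SAP. The AE-form Grade ≥3 incidence may therefore understate severe toxicity, and nothing in the SAP would show by how much.

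The illustration runs from no loss (61.5%) to 40.3%, and it rests on an assumed laboratory-only share of 0% to 100% of the minimum group. A reader might go further and infer that the result will be falsely favourable by a fixed margin, or that it cannot be compared with 61.5% or 70%. The documents do not support either statement; both are possibilities that laboratory tables would let a reader judge.

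The study tests no hypothesis, so no decision threshold is crossed. The change is still worth making, because the omission concerns the primary objective and the remedy is small.

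**What to change.** Keep the primary endpoint and the 8.3.7 reporting convention. In SAP 4.2.1, 4.2.2.2 and 5.1 add:

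1. The laboratory and vital-sign change summaries that the protocol already plans, including AESI item (e) of 9.4.
2. Worst post-baseline CTCAE grade and shift tables for haematology and for the chemistry parameters measured each cycle, using the evaluable denominators of 9.5.2.1, with exact 95% CIs for Grade ≥3.
3. A clearly labelled supportive incidence of patients with a Grade ≥3 AE or a Grade ≥3 laboratory value over the treatment-emergent window (to 90 days after the last dose).

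Reconcile 8.3.7 with Appendix B 1 so that all sites apply one rule.

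Item 1 only carries out the protocol. Items 2 and 3 go beyond its explicit outputs, and item 3 is a new supportive measure that should not replace the primary one. No new data are needed. The cost is a few more tables and a second figure that cannot be lower than the AE-form incidence when both use the same denominator, and so may look less favourable.

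Capture will still be incomplete and the report should say so. Scheduled samples on treatment days are taken before infusion, with extra draws only if clinically indicated. Some parameters (for example magnesium, gamma glutamyltransferase and coagulation tests) are required only at baseline or Day 1 and then as indicated.
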